### 3.2 Study measures and outcomes

Table 1: Measures and Timing

Variable (source) # = adolescent, * = parent	T0: Enrollment	T1: End of Intervention	T2: 4-week Follow up
Demographics##	X		
PROMIS Pediatric Global Health 7+2 or Parent Proxy Global Health 7+2#	X	X	X
PROMIS Pediatric Pain Interference or Parent Proxy Pain Interference#	X	X	X
Parent: (physical and emotional) PROMIS 29 Symptom Profile*	X	X	X
Hair Sample Collection##	X		X
Parent Experience of Providing Reiki*			X
Saliva collection##	Pre/post 2 Reiki sessions per week during weeks 1-4		
Medication Log#	Completed during weeks 0-4		
Parent intervention Log*	Completed during weeks 1-4		

Demographic form (T0) basic demographic information on both parent and adolescent.

Patient Reported Outcomes Measurement Information System (PROMIS), sponsored by the NIH. *PROMIS Pediatric Pain Interference* or *PROMIS Parent Proxy SF Pain Interference*, assesses how pain interferes with daily life for the adolescent. Well-validated measures show significant correlations between child and parent reports of pain. We will use the *PROMIS Pediatric Global Health 7+2* measure to obtain an overall evaluation score of the adolescents' physical and mental health. Both self-report and parent proxy versions are valid and reliable. Adult profile PROMIS 29 Symptom Profile (parent) assesses seven domains (depression, anxiety, physical function, pain interference, fatigue, sleep disturbance and ability to participate in social roles and activities).

Medication Log documenting all pain medications given one week prior to and during the intervention period.

Parent Intervention Log provided for parent record keeping. These logs will document Reiki session details, including the date, time, and length of session, interruptions to session, where the session took place, and parent comments and reactions (including adolescent reactions).

Hair collection and assay: Hair cortisol concentration (HCC) is a measure of chronic stress. A recent study found that the mean cortisol level assayed in 1 cm of hair was correlated ( $r=0.61$ ,  $p<0.01$ ) with the mean

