### **3.2.3 Data management**

Data will be collected using either paper measures or electronic measures via iPad per patient preference and/or internet availability. Data collected electronically will use Research Electronic Data Capture (REDCap) and entered by study staff into the study-specific electronic database for analysis. To minimize risks of disclosure of participants' personal information, the study site will ensure management and protection of materials and information in compliance with national, state and institutional guidelines for protection of confidentiality of health-related research information. Any paper measures will be checked for completeness during collection by the study team member collecting the data. The Medication Log and the Parent Intervention logs will be paper only. Study staff will collect a snapshot of the de-identified medication log and intervention log periodically in coordination with study visits. If the Medication Log is blank, parents will be asked if they have given any pain or anxiety medications during the previous period and have the parent fill out the log if needed. If the Intervention Log is blank or does not contain at least 5 entries for the previous week, parents will be asked about Reiki sessions and will fill out the log if needed. Data collected on paper will be scanned and emailed to the PI via secure email when each participating dyad has completed the follow-up visit. Data entered from paper measures will be entered into a database using double data entry and checking.

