## **3.3 Interventions**

This is a one-group feasibility study. There is only one intervention group. The Overall-Study PI and Local PI will recruit professional Reiki practitioners who are trained at Level 3 or Master Level and have prior experience working with families and children. A Reiki Master will perform the initial teaching and instruct the parent how to perform a simple 15-minute Reiki session. Parents will complete a return demonstration using light touch with their adolescent. The parent will receive an introductory book on Reiki, an informational article, and a poster showing hand positions for their reference as well as the intervention log to record sessions. The initial teaching session will take about 1.5 hours with breaks. The initial teaching session will be conducted by a Reiki Master and will mark the beginning of Week 1. A Reiki practitioner (Master or Level 3) will provide a shorter "booster" session the following week to review techniques with the parent and answer questions. This session will last 45 minutes with breaks. The "booster" session will count as one day for that week. Parents will be asked

to complete a minimum of 15 minutes of Reiki with their adolescent at least five days per week for the four-week intervention period. Parents will receive a phone call from the research coordinator once per week during weeks three and four to check in with them and ask if they have any questions or problems with the intervention and will refer to a Reiki practitioner if needed.

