**Adverse Events.** All adverse events (AEs) and serious adverse events (SAEs) will be tracked, documented, and reviewed. In one systematic review evaluating the efficacy of Reiki, nine randomized control trials reported no adverse events. It is anticipated that AEs in this study will be minimal. However, for the purpose of this study, AEs will be defined as clinically significant mental status changes, or any other unusual symptom or event (e.g. significant pain, a fall) that occur during the time frame of each Reiki session. An SAE will be defined as any untoward medical occurrence that results in death, is life threatening, results in hospitalization, or results in persistent or significant disability. Parent participants will be instructed to call the research coordinator for the study to report any adverse or unusual events. Parents will be instructed to call 911 in the event of a medical emergency and report the emergency to the research coordinator or the palliative care on-call medical provider (physician or nurse practitioner) when they are able. In either case, the research coordinator will consult with one of the palliative care physicians or nurse practitioners immediately in the case of an SAE or within 24 hours of an AE. The PI of the study will be notified of all AEs and SAEs immediately via email for AEs and text message and email for SAEs. All AEs and SAEs will be reported to the IRB in a timely manner.

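### Adverse-event detection rests mainly on parents volunteering reports: no scheduled contact asks a specific AE question and no rule has log comments read for AEs, so a low count would say little about safety

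*Combined protocol and SAP*

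**What the plan says.** Section 6.1 sets the aim: "All adverse events (AEs) and serious adverse events (SAEs) will be tracked, documented, and reviewed". Its means of detection is that "Parent participants will be instructed to call the research coordinator for the study to report any adverse or unusual events"; in an emergency, parents call 911 first and report afterwards. The coordinator then consults a palliative care physician or nurse practitioner, at once for an SAE and within 24 hours for an AE. Besides clinically significant changes in mental status, an AE is "any other unusual symptom or event (e.g. significant pain, a fall) that occur during the time frame of each Reiki session". The SAE definition is not tied to a session.

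Section 3.3 adds staff-initiated contact: "Parents will receive a phone call from the research coordinator once per week during weeks three and four". The coordinator is to "ask if they have any questions or problems with the intervention and will refer to a Reiki practitioner if needed".

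The Parent Intervention Log (Section 3.2 and Appendix 3) has one row per session, with columns for interruptions and for comments or reactions, including the adolescent's. Section 3.2.3 says: "Study staff will collect a snapshot of the de-identified medication log and intervention log periodically in coordination with study visits". The check it describes applies "If the Intervention Log is blank or does not contain at least 5 entries for the previous week"; parents are then asked about sessions and complete the log.

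Section 6.3 makes the two PIs responsible for monitoring participants for AEs. It also has a safety committee that meets quarterly to review any reports of untoward events.

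**The concern.** The aim in Section 6.1 is complete capture, but the step given to achieve it depends on the parent recognising an event and deciding to phone. In this population that is a demanding filter. Pain and tiredness are part of the illness, and the first part of Section 6.1 tells dyads to handle them in a session by pausing or changing position, without mentioning a report. The same section then gives significant pain as an example of an AE. A parent following the first instruction could reasonably not make the call that the second one needs.

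The later safeguards work on what has already been reported. The monthly monitoring in Section 6.3 B is described as checks of consent forms, data storage, data entry, accrual and completeness, with no AE listing. The safety committee recommends continuing or stopping on safety grounds, from the reports it receives. If events are missed at the start, nothing described downstream finds them. The results are also meant to inform a randomised trial (Section 4.1.1), and a low AE count could be carried into its planning as reassurance.

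**Working it through.** The plan states no AE rate, detection rate or safety precision, so there is no figure to reproduce. The check has two parts.

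**Each point where an event could be picked up, as the plan describes it**

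- Week 2 booster (3.2.1, 3.3): technique review and parents' questions. No AE question.
- Week 3 and Week 4 calls (3.3): a general prompt about questions or problems. The follow-up named is a Reiki practitioner, if needed. Section 6.1 is not mentioned.
- T1, end of Week 4 (3.2.1): measures repeated, in person or by phone. No AE question.
- T2, Week 8 (3.2.1): measures, hair sample, interview. No AE question. The interview guide as shown asks about training, use and symptoms, not harms.
- Table 1 (3.2): no AE row.
- Weeks 4 to 8: no participant contact is listed, although SAEs under 6.1 can occur at any time.
- Intervention Log (3.2.3): snapshots with visits, checked for blank or short logs. No instruction to read comments for AEs. Scanned paper data go to the PI only after a dyad finishes follow-up, too late for the 24-hour consultation in 6.1.

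Contacts after training: 5 per dyad x 12 = 60. Of these, 2 x 12 = 24 are the calls with a general prompt. The other 36 have no stated prompt about problems, although the booster invites questions.

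Planned sessions with a reaction field: 5 per week x 4 weeks x 12 dyads = 240 at the protocol minimum. Section 3.3 counts the booster as one of those days.

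**What a count of zero could show**

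The unit is the dyad, n = 12 (Section 4.1.1), and the outcome is at least one AE.

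With complete detection, the exact one-sided 95% upper bound for 0 of 12 is 1 - 0.05^(1/12) = 22.1%. The upper limit of the two-sided 95% interval is 1 - 0.025^(1/12) = 26.5%.

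Now let s be the share of affected dyads whose event reaches the coordinator. The documents give no value, so s is an assumption, shown over a range. The bound becomes 0.221/s. With true per-dyad risk p, the chance of recording no affected dyad is (1 - p x s)^12, shown here for an assumed p of 20%.

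| s (assumed) | Upper bound on risk after 0 of 12 | Chance of recording none if p = 20% |
|---|---|---|
| 1.00 | 22.1% | 0.80^12 = 6.9% |
| 0.75 | 29.5% | 0.85^12 = 14.2% |
| 0.50 | 44.2% | 0.90^12 = 28.2% |
| 0.25 | 88.4% | 0.95^12 = 54.0% |

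The first row reflects sample size alone. The other rows show what incomplete detection would add.

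**The case against.** A reader might infer that AEs can surface only if a parent phones, that staff never ask, and that the check-in calls divert harms to a Reiki practitioner in conflict with Section 6.1. The documents do not support that. The Week 3 and 4 calls are started by staff and ask about problems, which could bring out an AE. Referral to a practitioner is only if needed. The caller is the same coordinator who must consult a palliative clinician about an AE, so an event raised on a call is not barred from that route. Staff collect the logs, and Section 6.3 gives the PIs a monitoring duty and requires team members to tell them of AEs immediately. Section 3.2.3 does not say that its completeness check is the only use of the log. What is missing is a stated link from calls and logs to AE assessment; the two routes do not contradict each other.

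A reader might also infer that the trial plans to declare the intervention safe. It does not: safety is not a listed outcome, and Section 4.1.1 speaks of informing the next trial's sample size. With 12 dyads, no strong safety conclusion is possible even with perfect capture.

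Two further points have weight. The AE definition is narrow and session-bound, so ordinary tiredness that goes unreported is not clearly a missed AE, and the gap after Week 4 matters mainly for SAEs. The interview guide as shown may also be incomplete, so its silence on harms is weak evidence.

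These points limit the claim but do not remove it. A general prompt in two of the four intervention weeks, an unread comment field and a duty without a method do not amount to a detection procedure.

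**Conclusion.** The point holds in limited form. AE detection relies mainly on spontaneous parent reports. No scheduled contact has a specific AE question, and no rule says that log comments, or problems raised on the calls, are assessed as AEs. Carried out as written, the plan is likely to under-count. The amount cannot be estimated from the documents; the table's detection shares and 20% risk are assumptions for illustration.

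The one figure that needs no assumed detection share is the 22.1% upper bound for 0 of 12, which assumes complete detection and independent dyads with a common risk. Few or no reported AEs should therefore not be presented as evidence of safety, first because of n = 12 and further because capture is incomplete. The feasibility and acceptability outcomes are not affected. The change is worth making because the needed contacts and records are already in the plan.

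**What to change.** - **Sections 3.2.1, 3.3 and Table 1:** add one fixed AE/SAE question, asked for both adolescent and parent, at the booster, the Week 3 and Week 4 calls, T1 and T2. At T2 it should cover the whole period since T1.
- **Section 3.2.3:** have the coordinator read the log comments and interruptions at each planned snapshot and record any entry that meets the protocol's AE definition. State when snapshots are taken, since T1 may be by phone.
- **Section 3.3:** state that anything raised on a call that meets that definition enters the existing Section 6.1 route. This adds no new clinical referral rule.
- **Sections 6.1 and 6.3 C:** reconcile the definitions. Section 6.1 defines AEs by events during a session and SAEs by outcomes that include hospitalisation. Section 6.3 C lists allegations of injury or improper consent as AEs, and lists death, attempted suicide, major depression and breach of confidentiality as SAEs. Also reconcile the Section 6.1 handling of pain in a session with its AE example of significant pain. Which definition applies is for the investigators to decide; the question and the log review need a single one.
- **Section 4.1:** report solicited and spontaneous AEs separately, as dyads affected out of 12 with exact intervals, and state how events were sought.

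The cost is a short script and some reading time at contacts and snapshots already planned, with no added visits. More minor or illness-related events will be recorded; separate reporting keeps them interpretable.

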## 6.2 Benefits

The adolescent and/or parent may experience feelings of relaxation and/or decreased stress.

## 6.3 Monitoring

### A. Study monitoring.

Because this is a small, one-site, low-risk pilot study, the PI will be responsible for the ongoing evaluation of the progress of the proposed research study. The overall PI and local PI will ensure that all eligibility criteria and consent requirements are met prior to a participant's participation and that all study procedures and AE reporting occur according to the IRB-approved protocol. The Ohio State University College of Nursing has created a Safety Monitoring Committee (SMC). This group will meet quarterly once recruitment has begun to review the study and any reports of untoward events and to monitor their resolution. Minutes will be kept of all meetings and following SMC meetings, the results of the meeting (meeting minutes) concerning possible negative side effects will be documented and sent to the Overall Study PI, Local PI, and the IRB. The local PI's IRB will advise and monitor the design and implementation of all safety monitoring and risk management procedures.

### B. Procedures:

- 1) Monitoring study safety to include monitoring schedule, and auditing selected cases for compliance with IRB requirements, conformance with informed consent requirements, verification of source documents, and investigator compliance.

Monitoring of study safety will occur monthly. Monitoring will begin with the first participant recruited. To ensure reliability of data entry, the Overall study PI will review a random sample of cases and compare the results with the information recorded in the database to monitor for compliance with IRB requirements. The Overall study PI will look at consent forms, data storage, and correct entries. An acceptable error rate is less than 3%, i.e., 3 per 100 entries. If error rate is more than 3%, the Overall study PI and a second member of the study team will recheck all data.

Quality assurance reports will be prepared on a monthly basis by the Overall study PI and reviewed by Local PI. The reports will inform about missing, invalid, or inconsistent data on selected key variables such as age, sex, or diagnoses. The statistician on the project will oversee preparation of the reports. The reports will contain a summary of monthly accrual and cumulative accrual, a summary of key characteristics of the study participants, a summary of the completeness and quality of data.

Quality assurance will involve engaging in good data management activities. Procedures that include checking the integrity of data storage and examining frequency distributions to look for data anomalies.

- 2) Minimizing research-associated risk: This study poses minimal risk to participants.

Consent Procedures. Local PI, a research coordinator or another member of the study team will introduce the study to the adolescent and parent. Recruitment methods used by this palliative care center for previous studies will be used; these include approaching potential participants during regular clinic visits or mailing study information followed by up to three phone calls. If the study is introduced in the clinic, a member of the study team will introduce the study, and if the adolescent and parent are interested, a research coordinator will give more details about the study, go over the

consent form, answer any and all questions. If by mail, interested participants who meet criteria will call the palliative care center and the research coordinator will mail a packet with the consent form and study information and will schedule a phone call to discuss the study. The research coordinator will meet with the parent and adolescent either in the clinic or in the home to go over the consent form. Any and all questions will be answered before the parent gives written consent and the adolescent gives written assent, or consent if age 18 or over, if able. Adolescent-parent dyads that meet eligibility criteria and give appropriate consent will be able to participate in the study. To protect participant confidentiality, the research coordinator will discuss consent in a private room at in the clinic, hospital room, or patient's home. To prevent undue coercion, potential participants will be instructed that participation is completely voluntary, that their decision to participate will not affect their treatment, and that they may discontinue their participation in the study at any time. If the potential subject refuses to participate, there will be no further recruitment efforts but the subject will be asked about their reasons for refusal.

Risk of measures: It is possible that the adolescent or parent may become fatigued while completing consent or baseline measures that they may become fatigued. Participant burden was considered very carefully due to the nature of this study. Study measures to address the constructs were carefully chosen to minimize undue burden or fatigue.

Fatigue. To minimize fatigue, the adolescent and parent will be offered breaks during the study procedures. Participants may choose to discontinue any procedure at any time for any reason. If at any point the adolescent or parent becomes fatigued or the adolescent requires attention, we will either take a break or stop altogether depending on the preference of the adolescent or parent.

3) Protecting the confidentiality of participant data:

Risk of breach of confidentiality: There is a possibility of risk of breach of confidentiality of protected health information. The Overall study PI and the Local PI will take all necessary steps to ensure that this does not happen. All participants will be assigned an ID code upon entry into the study. All records relating to the participant's involvement in this research study will be stored securely within a locked office. Participant identities on these records are indicated by an ID code rather than by a name, and the file linking these ID codes with their identity are kept separate from the research records. Screening and enrollment logs will be kept securely password-protected on the server and de-identified when shared with Overall PI. Only the research coordinators will have the information to link the special ID codes to the participant's names. The master list will be kept in a password protected file on the protected server. No information will be used in subsequent publications that would identify individual participants.

This study does not involve evaluating drugs or devices.

Adequacy of Protection Against Risks: Efforts will be taken to minimize the risk to breach of confidentiality of data and anonymity of the participants. All participants will be assigned a unique ID code number under which all data will be stored. Security of the data will be upheld through the use of password protection, encryption, and restricted access to users. Consent forms and a list of the match between participant names and code numbers will be retained securely in a locked office area.

C. Procedures for identifying, reviewing, and reporting AEs and unanticipated problems to the IRB, funding sources, and FDA (if applicable). If applicable, the type and number of events that would halt accrual and

would generate a review of eligibility, monitoring, assessments, intervention, and how the resumption of accrual would occur.

Throughout the study the Overall study PI and Local PI will be responsible for monitoring participants for adverse events. The following will be considered SAEs: patient death, attempted suicide, major depression, or breach of confidentiality. The following will be considered AEs: patient allegations of physical/mental injury during the study, patient allegation of inappropriate consenting or recruitment procedures. The Overall study PI and Local PI will review AEs and unanticipated problems within 24 hours of notification of the event. Unanticipated problems that are SAEs will be reported within one week of the investigator becoming aware of the problem. Any other unanticipated problems should be reported within two weeks of the investigator becoming aware of the problem. All fatal or serious/life threatening AE will be reported to the IRB in accordance with IRB policy. Non-serious AEs will be reported to the IRB at time of continuing review. AEs determined as anticipated problems involving risks to subjects or others will be reported to IRB at time of continuing review. The Overall study PI and Local PI will be informed by team members about any AEs or unanticipated problems immediately. If protocol changes are needed, the research coordinator, with Overall study PI and Local PI approval, will submit a modification request to the IRB. Protocol changes will not be implemented prior to IRB approval unless necessary to eliminate apparent immediate hazards to the participants.

At each meeting of the SMC during the conduct of the trial, the SMC will make a recommendation to the Overall study PI to continue or to terminate the trial. This recommendation will be based on safety considerations. The Overall study PI is responsible with the SMC for safeguarding the interests of participants and for the conduct of the trial. The Overall study PI will be responsible for deciding whether to continue or to stop the trial based on the SMC recommendations.

- D. For multi-site studies, procedures to ensure compliance with the monitoring plan and reporting requirements across study sites.

This is a single site study.

- E. An assessment of external factors or relevant information (i.e., developments in the literature, results of related studies) that may have an impact of the safety of participants or on the ethics for the research study.

The Overall study PI will be responsible for reviewing the literature monthly and reviewing with Local PI and inform the study team of any new developments related to the study that may have impact on the safety of participants or the ethics for the research study.

- F. The advanced plans for interim and/or futility analysis.

An interim analysis will occur at six months after study initiation to determine whether enrollment is adequate or if a revision in recruitment strategies is needed and/or if the study appears to be futile (no participants recruited during six months of active recruitment). The Overall study PI together with Local PI will determine if early closure is justified if anticipated accruals cannot meet stated study goals.

- G. Description of how often monitoring entity meets, who will record proceedings, what group(s) receives SMC reports, and time period for completing reports should be specified.

The Overall study PI, and Local PI and study staff will meet every two weeks either in person or by phone. The research coordinator will document meeting proceedings. The SMC will meet quarterly.

